1.14 EXCLUSION CRITERIA

1. Subjects receiving chronic hemodialysis with a vascular catheter.
2. Subjects with vascular access that is determined by the clinician to be unacceptable for a hemodialysis procedure.
3. Patients with a bleeding diathesis
4. Patients receiving anti-coagulants
5. Previous vascular access surgery (≤ 30 days from study entry) or planned access surgery
6. Known hypersensitivity to any imaging agents (e.g., contrast) that may be required during the study period
7. Patients with confirmed vasculitis
8. Vascular access infection or systemic active infection within 30 days of study entry
9. Life expectancy less than 12 months
10. Planned renal transplantation or planned conversion to peritoneal dialysis
11. Subjects with any condition determined by the investigator that precludes them from safely participating in the study.
12. Female participants at the time of consent to the study cannot be breastfeeding or pregnant.

1.15 PRIMARY SAFETY MEASURE

Rate of serious adverse device events (SADEs)

1.16 ADDITIONAL SAFETY MEASURES

- Rate of adverse events (AEs)

- Rate of serious adverse events (SAEs)
- Rate of adverse device events (ADEs)
- Rate of adverse procedure events (APEs)
- Rate of serious adverse procedure events (SAPEs)

1.17 PRIMARY PERFORMANCE MEASURES

Percentage of successful hemodialysis sessions with the Hemotek device.

1.18 SECONDARY PERFORMANCE MEASURES

No powered secondary performance measures are planned.

1.19 ADDITIONAL PERFORMANCE MEASURES

- Machine alarm rate (blood alarms only) during hemodialysis therapy, including false alarms and relationship of alarm to venous needle
- Changes to blood flow rate setting during therapy sessions and relationship to venous needle
- Venous, transmembrane, and/or arterial pressure measurements
- Patient survey including ratings for venous needle comfort and feelings of safety (V Needle only)
- Clinician survey, evaluating the following items:
 - use of the device according to the instructions for use (IFU)
 - ability to properly cannulate
 - ability to objectively see flashback
 - confirmation that the footplate is fully depressed (V Needle only)
 - feelings regarding patient risk (V Needle only)
- Achieved treatment time
- Achieved blood flow rate
- Ability to cannulate fistula
- Episodes of partial or complete needle dislodgment

1.20 STUDY DESIGN

The study is an open-label, non-randomized, single arm, multi-center trial with subject's serving as their own control. For the first three (3) control sessions, subjects will undergo usual hemodialysis sessions with a commercially available device. For the remaining six (6) sessions, subjects will be cannulated with a V Needle in place of a usual venous line AV fistula set.

The hemodialysis sessions will be conducted in the clinic. Subjects will be observed by a clinician for the duration of each session. Clinicians will monitor the session for any abnormal disruptions, therapy interruptions, and/or adverse events, including hemolysis, due to V Needle presence. All machine blood alarms, therapy interruptions, and/or partial or complete needle

dislodgements will be recorded and immediately corrected. Clinicians will be responsible for identifying adverse events as they occur and will activate established facility emergency response plans if necessary. A clinician will perform cannulation.

Cannulation site and surrounding tissue will be examined by the nurse and assessed for any locally induced trauma before and after treatment.

A survey will be completed by the clinicians and patients to assess usability, comfort, and feelings of safety of the V Needle.

1.21 SAMPLE SIZE JUSTIFICATION

The sample size was determined to compare the rate of successful treatments between hemodialysis sessions with the test needle compared to the control needle.

The hypothesis test for the primary performance measure is defined as follows:

$$H_0: p_T - p_C \leq -\delta$$

$$H_1: p_T - p_C > -\delta$$

where p_T is the probability of a successful hemodialysis treatment session with the V Needle (test), p_C is the probability of a successful hemodialysis treatment session with a commercially available device (control), and δ is the non-inferiority margin.

This sample size estimation is based on the following assumptions:

- The expected success rate for both devices is 98%
- The expected difference between the test and control treatment groups is 0%
- There is a test-to-control sampling ratio of 2:1
- A non-inferiority margin of 8% ($\delta = 0.08$)
- Use of a one-sided Farrington-Manning Score Test with 85% power and at a one-sided 2.5% significance level

Based on these assumptions, a statistically powered sample size of 87 test (V Needle) sessions is required for the primary endpoint^{1,2}.

The total sample size is therefore determined to be 108 test sessions with 18 subjects required to account for 20% attrition and/or any of the 6 V Needle sessions being missed.

The primary performance analysis will test the non-inferiority hypothesis as a difference of proportions between the test and control groups using a one-sided Farrington-Manning Score Test at a significance level of $\alpha=0.025$.

¹ Chow, S.C., Shao, J., and Wang, H. 2008. Sample Size Calculations in Clinical Research, Second Edition. Chapman & Hall/CRC. Boca Raton, Florida.

² Farrington, C. P. and Manning, G. 1990. 'Test Statistics and Sample Size Formulae for Comparative Binomial Trials with Null Hypothesis of Non-Zero Risk Difference or Non-Unity Relative Risk.' Statistics in Medicine, Vol. 9, pages 1447-1454.

Additionally, the primary performance measure will be analyzed on the subject-level (utilizing a non-inferiority margin of 0.05) by testing the difference in mean success rates per subject across treatment groups using a one-sided paired t-test at a significance level of $\alpha=0.025$.

1.22 STUDY TIMELINE

Month 0: Site identification and IRB approvals; study start-up and training

Month 2: First patient enrolled

Month 5: Last patient enrolled

Month 6: Data analysis

Month 7: Completion of study report

1.23 SCHEDULE OF ACTIVITIES (SOA)

Table 1: Schedule of Activities

	Enrollment Visit	Control Dialysis Sessions (Visit 1-3)	Test Dialysis Sessions (Visit 4-9)	Final Study Visit (7-10 days after Visit 9)
Informed Consent	X			
Inclusion/Exclusion	X			
Demographics	X			
Medical History Form	X			
Vital Signs	X			
Adverse Event Form	X	X	X	X
Therapy Assessment Form, including the following: 
• Treatment success/failure• Blood alarms• Flow rates• Prescribed treatment time• Achieved treatment time• Prescribed blood flow rate• Achieved blood flow rate• Ability to cannulate fistula		X	X	
Patient Survey			X	
Clinician Survey		X	X	

1.24 STUDY PARTICIPANT DURATION

It is expected that the visits will occur at sequential dialysis sessions such that the patient participation is limited to an enrollment visit and then approximately three (3) weeks of follow-up visits. No windows are provided for these visits, but the entire sequence shall occur within 40 days from the baseline visit.

2 Statement of Compliance

The trial will be carried out in accordance with International Conference on Harmonisation Good Clinical Practice (ICH GCP) and the following:

- United States (US) Code of Federal Regulations (CFR) applicable to clinical studies (45 CFR Part 46, 21 CFR Part 50, 21 CFR Part 56, 21 CFR Part 312, and/or 21 CFR Part 812)

National Institutes of Health (NIH)-funded investigators and clinical trial site staff who are responsible for the conduct, management, or oversight of NIH-funded clinical trials have completed Human Subjects Protection and ICH GCP Training.

The protocol, informed consent form(s), recruitment materials, and all participant materials will be submitted to the Institutional Review Board (IRB) for review and approval. Approval of both the protocol and the consent form must be obtained before any participant is enrolled. Any amendment to the protocol will require review and approval by the IRB before the changes are implemented to the study. In addition, all changes to the consent form will be IRB-approved; a determination will be made regarding whether a new consent needs to be obtained from participants who provided consent, using a previously approved consent form.

Investigator Name (please print):

Investigator Signature:

Date:

3 Introduction

3.1 Study Rationale

In patients undergoing hemodialysis for the treatment of end-stage renal disease, Venous Needle Dislodgement (VND) is a rare, but potentially fatal situation in which the needle delivering a patient's blood back to the body after filtration by a dialysis machine becomes inadvertently disconnected from the patient. Hemotek Medical Inc. has developed the V Needle, a venous needle return that is designed to reduce patient risk from exsanguination-related injury or death. This clinical study will serve as a confirmatory study to gain FDA marketing clearance of the Hemotek V Needle system in the clinical setting. During this study, we will determine the ability of the V Needle to successfully deliver appropriate hemodialysis therapy per the facility's guidelines. It will also be used to determine if the V Needle triggers false blood alarms under normal operating conditions. This study will also be used to demonstrate the V Needle meets effective usability criteria. Rates of adverse events and ability to complete the hemodialysis session will be compared to the rates recorded using commercially available devices during the hemodialysis sessions prior to the use of the Hemotek V Needle.

3.2 Background

Every week in the US, more than 500,000 patients collectively undergo $>1,500,000$ dialysis sessions which is equivalent to $> 70,000,000$ dialysis sessions per year, each about 3 hours long. A potentially devastating complication of hemodialysis is venous needle dislodgement (VND) whereby the needle returning blood into a patient's body accidentally becomes withdrawn from the arm. If undetected, the blood loss quickly becomes injurious or, worse, can lead to death.

A device that aims to detect VND, but does not disrupt the flow of the dialysis machine, is the RedSense device. The device uses an optical sensor to activate a light and sound alarm when a VND is detected. For this device, the alarm functioned correctly in 92.5% of tests, and after device modification, the device operated in 97.2% of tests³.

While the RedSense device can trigger an alarm when a VND occurs, there is no single, inexpensive and easy-to-use method that can both detect VND and immediately shut down the flow of blood through the needle. To address this glaring need in the dialysis marketplace, Hemotek has developed the V Needle, a single-use disposable needle with built-in VND protection. It has an elegant mechanical mechanism that is designed to automatically occlude the flow of blood during dislodgement and trigger the dialysis machine pump to shut down.

³ Ahlmen et al., 2008. "A new safety device for hemodialysis" Hemodialysis International 2008; 12:264–267.

3.3 Risk/Benefit Assessment

3.3.1 Known Potential Risks

Risks related to the study and/or device are expected to be the same as those risks for patients undergoing hemodialysis. Due to the design of the V Needle, very slight increases in certain risks are potentially possible but are not expected.

The potential risks specifically associated with the V Needle are as follows:

- Improper needle function, leading to machine false alarms or changes to dialysis blood flow rate or pressure
- Difficulty inserting the needle into the veins (cannulation)
- Slightly increased risk of blood loss and/or air embolism

The risks associated with all AV fistula sets are as follows:

- Air in the tubing/blood vessels, which could result in blockage and reduced blood flow in that vessel or other vessels in the body
- Allergic responses to the device materials, such as swelling, itchiness, or inflammation of the skin
- Small particles released into the blood vessels, which could result in blockage and reduced blood flow in that vessel or other vessels in the body
- Improper function of the device, leading to delay in therapy
- Infection
- Breakdown of blood cells due to unstable blood flow (hemolysis), which can lead to fatigue, dizziness, and headaches
- Blood loss
- Blood leaks into surrounding tissue, leading to swelling and/or pain (infiltration, when the needle tip is placed into the body but not directly into the blood vessel)
- Injury from sharp needle

3.3.2 Known Potential Benefits

The primary benefit for participation in the study is to have access to a new device that can potentially detect VND. Additionally, future patients may benefit from this potentially life-saving device, and the knowledge gained about the device and study design in this study are required first steps in bringing the device to market.

3.3.3 Assessment of Potential Risks and Benefits

The risks to study subjects beyond those normally associated with hemodialysis are due to the slight force from the footplate on the access site and the presence of the flexible membrane inside the V Needle. There may be a slightly increased risk of blood loss and/or air embolism, but based on laboratory testing and subject matter expert input, these harms are not expected to occur more frequently than in usual dialysis sessions. Due to the potentially improved safety profile through the use of the device and potential for bringing a potentially life-saving device to market, the value of the knowledge gained through this study are judged to outweigh the risks incurred by study participation.

4 Objectives and Endpoints

The study is designed to confirm the safety, performance, and usability of the Hemotek V Needle A.V. Fistula Set for temporary cannulation for hemodialysis in the treatment of end-stage renal disease patients in the clinical setting.

Because the objective of the study is confirmation of safety, performance, and usability, a number of endpoints are collected to ensure that the safety, performance, and usability of the device can be evaluated.

4.1 PRIMARY SAFETY MEASURE

Rate of serious adverse device events (SADEs)

4.2 ADDITIONAL SAFETY MEASURES

- Rate of adverse events (AEs)
- Rate of serious adverse events (SAEs)
- Rate of adverse device events (ADEs)
- Rate of adverse procedure events (APEs)
- Rate of serious adverse procedure events (SAPEs)

4.3 PRIMARY PERFORMANCE MEASURES

Percentage of successful hemodialysis sessions with the Hemotek device.

4.4 ADDITIONAL PERFORMANCE MEASURES

- Machine alarm rate (blood alarms only) during hemodialysis therapy, including false alarms and relationship of alarm to venous needle
- Changes to blood flow rate setting during therapy sessions and relationship to venous needle
- Venous, transmembrane, and/or arterial pressure measurements
- Patient survey including ratings for venous needle comfort and feelings of safety (V Needle only)
- Clinician survey, evaluating the following items:
 - use of the device according to the instructions for use (IFU)
 - ability to properly cannulate
 - ability to objectively see flashback
 - confirmation that the footplate is fully depressed (V Needle only)
 - feelings regarding patient risk (V Needle only)
- Achieved treatment time
- Achieved blood flow rate
- Ability to cannulate fistula

- Episodes of partial or complete needle dislodgment

5 Study Design

5.1 Overall Design

This study is a prospective, multi-center, single-arm study with subjects acting as their own control designed to confirm the safety, performance, and usability of the V Needle, a new safety needle for use during in-clinic hemodialysis that is designed to automatically generate a partial occlusion of the internal fluid path and trigger the hemodialysis machine to alarm and shut off if a complete dislodgement of the venous needle from the arm inadvertently occurs.

For the first three (3) control sessions, consenting subjects will undergo usual hemodialysis sessions with a commercially available device. For the remaining six (6) test sessions, subjects will be cannulated with a V Needle in place of a usual venous line AV fistula set.

The hemodialysis sessions will be conducted in the clinic. Subjects will be observed by a clinician for the duration of each session. Clinicians will monitor the session for any abnormal disruptions, therapy interruptions, and/or adverse events, including hemolysis, due to V Needle presence. All machine blood alarms, therapy interruptions, and/or partial or complete needle dislodgements will be recorded and immediately corrected. Clinicians will be responsible for identifying adverse events as they occur and will activate established facility emergency response plans if necessary. A clinician will perform cannulation.

Cannulation site and surrounding tissue will be examined by the nurse and assessed for any locally induced trauma before and after treatment.

A survey will be completed by the users to assess usability of the V Needle.

After the first five (5) patients will be enrolled, and data through the last visit of the fifth patient is available, this data will be submitted to the FDA while study enrollment and visits continue. No Hemotek Medical V Needle treatments will occur until after FDA has reviewed the data from the first 5 patients and allows the study to proceed. Data will also be submitted to the FDA after the tenth patient completes their last visit and data is available. After the tenth patient, study enrollment and visits can continue, but no Hemotek Medical V Needle treatments will occur on the final 5-10 patients until the FDA allows the study to proceed. After FDA has found the data for the first 10 patients acceptable, the rest of the study can continue until the end.

At least two different clinicians will evaluate the device for each patient and for each needle for that patient (test and control) to minimize the bias associated with the same clinician evaluating all of the sessions for a given subject.

5.2 Scientific Rationale for Study Design

The study is designed to confirm the safety, performance, and usability of the V Needle, a new medical device. The device will be tested by comparing the ability to successfully complete hemodialysis sessions to commercially available devices as determined by a clinician.

Additionally, the rates of adverse events will be compared to rates measured using commercially available devices, providing a comparator with data collected under similar circumstances and in the same patient population.

5.3 End of Study Definition

A participant is considered to have completed the study if they have completed all follow-up visits. It is expected that 15 subjects will undergo 9 treatments each. In the event that some of these patients do not complete the full set of treatments, additional subjects (up to 20 total) will be recruited until 87 V Needle treatments are completed and all patients have completed their study visits.

After the first five (5) patients will be enrolled, and data through the last visit of the fifth patient is available, this data will be submitted to the FDA while study enrollment and visits continue. No Hemotek Medical V Needle treatments will occur until after FDA has reviewed the data from the first 5 patients and allows the study to proceed. Data will also be submitted to the FDA after the tenth patient completes their last visit and data is available. After the tenth patient, study enrollment and visits can continue, but no Hemotek Medical V Needle treatments will occur on the final 5-10 patients until the FDA allows the study to proceed. After FDA has found the data for the first 10 patients acceptable, the rest of the study can continue until the end.

If there are any deaths or three SADEs during the study device period that require medical or surgical intervention, study enrollment and further visits will be stopped, and an assessment (in conjunction with the DSMB and FDA) will be enacted.

6 Study Population

6.1 Inclusion Criteria

In order to be eligible to participate in this study, an individual must meet all of the following criteria:

1. Subjects with end-stage renal disease receiving chronic hemodialysis in a clinical setting.
2. Subjects must be able to receive hemodialysis with the Hemotek 15-gauge, 1 inch length V Needle, with 12 inch tubing.
3. Age greater than 18 years old at screening.
4. Vascular access via a mature arteriovenous (AV) fistula or graft in the arm and determined to be adequate for a chronic hemodialysis therapy.
5. AV fistula has already been demonstrated to adequately permit one or more hemodialysis sessions.
6. Subject prescribed blood flow rates between 200 ml/min and 450 ml/min
7. In women with child-bearing potential, negative urine or serum pregnancy test at Screening.
8. Subject able to communicate effectively with investigative staff, competent and willing to give written informed consent, and able to comply with entire study procedures.
9. Hemoglobin ≥ 9 g/dL (consistent with KDOQI guidelines)

10. Normal platelet count ($\geq 150,000 /mm^3$)
11. International Normalized Ratio (INR) ≤ 1.5

6.2 Exclusion Criteria

An individual who meets any of the following criteria will be excluded from participation in this study:

1. Subjects receiving chronic hemodialysis with a vascular catheter.
2. Subjects with vascular access that is determined by the clinician to be unacceptable for a hemodialysis procedure.
3. Patients with a bleeding diathesis
4. Patients receiving anti-coagulants
5. Previous vascular access surgery (≤ 30 days from study entry) or planned access surgery
6. Known hypersensitivity to any imaging agents (e.g., contrast) that may be required during the study period
7. Patients with confirmed vasculitis
8. Vascular access infection or systemic active infection within 30 days of study entry
9. Life expectancy less than 12 months
10. Planned renal transplantation or planned conversion to peritoneal dialysis
11. Subjects with any condition determined by the investigator that precludes them from safely participating in the study.
12. Female participants at the time of consent to the study cannot be breastfeeding or pregnant.

6.3 Screen Failures

Individuals who sign informed consent, but are then discovered to not meet the inclusion and exclusion criteria and/or who do not complete the Control Dialysis Sessions will be considered screen failures. These subjects will not be included in the subject count. Information about the subject's demography, screen failure details, eligibility criteria, and any adverse events that occur prior to screen failure will be collected. Subjects who are screen failures may be rescreened if deemed appropriate (e.g., they need to allow their fistula to mature). Rescreened subjects should be assigned their original patient number.

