9.1.2 Control Dialysis Sessions

The assessment of the ability to successfully complete the session will be determined by the clinician and recorded on the Therapy Assessment Case Report Form (CRF). The actual treatment time will also be recorded. Adverse events will be recorded on an Adverse Event Case Report Form. Photos of the cannulation may be taken.

Additional performance measures include the following:

- Machine alarm rate (blood alarms only) during hemodialysis therapy, including false alarms and relationship of alarm to venous needle
- Changes to blood flow rate setting during therapy sessions and relationship to venous needle
- Venous, transmembrane, and/or arterial pressure measurements
- Clinician survey, evaluating the following items:
 - use of the device according to the instructions for use (IFU)
 - ability to properly cannulate
 - ability to objectively see flashback
- Achieved treatment time
- Achieved blood flow rate
- Ability to cannulate fistula
- Episodes of partial or complete needle dislodgment

In the event that the venous needle becomes 1) completely dislodged, or 2) partially dislodged and the venous pressure increases by more than 40 mm Hg indicating some disruption of the fluid flow, the event should be recorded on the therapy assessment and AE CRFs and appropriate laboratory tests (including CBC, plasma hemoglobin concentration, serum electrolytes) shall be obtained.

Patients shall be monitored for symptoms of hemolysis; if hemolysis is suspected, an AE form should be completed and appropriate laboratory tests (including CBC, plasma hemoglobin concentration, serum electrolytes) shall be obtained.

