10.1.2 Primary Hypothesis

The primary performance goal for this study is that the Hemotek device will provide successful hemodialysis treatment at a rate non-inferior to that of the commercially available devices. The rate of successful treatment will be computed as the number of successful session completions of V Needle, as determined by the clinician, divided by the total number of sessions attempted.

To determine whether a dialysis session was successful, clinicians will be asked “Was dialysis session incomplete because of a vascular access issue?” If the answer is “No,” this indicates that the dialysis session completed successfully or was stopped for reasons that were not related to the vascular access (e.g., patient illness, etc.).

The null hypothesis is that the difference between the rates of successfully completed hemodialysis sessions for the test and control groups is less than or equal to the non-inferiority margin (indicating inferior success rate). Rejection of the null hypothesis indicates the observed data supports the alternative hypothesis that the difference between the rates of successfully completed hemodialysis session for the test and control groups is at least the non-inferiority margin (indicating non-inferior success rate).

The hypothesis test for the primary analysis are defined as follows:

$$H_0: p_T - p_C \leq -\delta$$

$$H_1: p_T - p_C > -\delta$$

where p_T is the probability of a successful hemodialysis treatment session with the V Needle (test), p_C is the probability of a successful hemodialysis treatment session with a commercially available device (control), and δ is the non-inferiority margin.

⁴ Chow, S.C., Shao, J., and Wang, H. 2008. Sample Size Calculations in Clinical Research, Second Edition. Chapman & Hall/CRC. Boca Raton, Florida.

⁵ Farrington, C. P. and Manning, G. 1990. 'Test Statistics and Sample Size Formulae for Comparative Binomial Trials with Null Hypothesis of Non-Zero Risk Difference or Non-Unity Relative Risk.' Statistics in Medicine, Vol. 9, pages 1447-1454.

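### Section 6.3 as written can take a control failure, with that subject's control sessions, out of the primary comparison while test failures stay in, and Section 10.2 defines no analysis set to settle it

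*Combined protocol and SAP*

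**What the plan says.** Section 6.3 has two limbs. Consented subjects found ineligible are screen failures, and so are those covered by the second limb: "and/or who do not complete the Control Dialysis Sessions will be considered screen failures. These subjects will not be included in the subject count". For all of them, "Information about the subject's demography, screen failure details, eligibility criteria, and any adverse events that occur prior to screen failure will be collected". Whether their control sessions succeeded or failed is not on that list. The section also allows rescreening.

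The primary endpoint is built on completion too. Under Section 10.1.2 the clinician is asked "Was dialysis session incomplete because of a vascular access issue", and a yes is a failure. The success rate is the number of successes "divided by the total number of sessions attempted". Section 9.1.2, which describes the control sessions, says: "The assessment of the ability to successfully complete the session will be determined by the clinician".

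Test sessions have no rule like the second limb of 6.3. Under Section 5.3, if subjects do not finish their treatments, "additional subjects (up to 20 total) will be recruited until 87 V Needle treatments are completed". Section 8.1 says that stopping one visit is not leaving the study. Section 8.2 permits use of data up to withdrawal. Section 10.3.1 pools sessions by needle type, and Section 10.4.2 uses available data without imputation. Section 10.2 is titled for analysis populations but holds only one sentence on consistency across subgroups.

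**The concern.** The control success rate is half of the non-inferiority comparison, and it rests on 45 to 60 sessions (three each from 15 to 20 subjects). If the rule for who counts depends on how the control sessions went, the comparator is selected on its own outcome. Control failures leave together with their subjects, new subjects fill the places, and V Needle failures stay in.

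The text allows two readings of the second limb of 6.3:

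- **Attendance.** Table 1 uses "Control Dialysis Sessions (Visit 1-3") as the name of a block of visits. On this reading 6.3 catches only subjects who leave before the third control visit, and the subject count may mean no more than the recruitment target.
- **Completion.** Sections 9.1.2 and 10.1.2 use completing a session for the outcome itself. On this reading one control session cut short by an access problem can make the subject a screen failure.

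The attendance reading does not close the gap. A subject whose access fails during a control session and who therefore never finishes the control period is a screen failure on both readings. The plan does not say whether the failed session is then analysed.

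**Working it through.** **Inputs.** From Section 10.1.1: 98% success on both needles, margin 0.08, one-sided Farrington-Manning score test at 0.025, 85% power, 2:1 ratio, 87 test sessions. From Section 10.3.1: 3 control and 6 test sessions per subject, 108 and 54 sessions from 18 subjects. From Sections 1.11 and 5.3: 15 to 20 subjects.

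**The plan's own figure.** Exact binomial enumeration of the score test (restricted maximum likelihood variance) gives 85.5% power at 87 test and 44 control sessions, and 85.3% at 87 and 43. The stated 87 is reproduced, so the same method is used below.

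**How often the question arises.** The chance that a subject has at least one control failure is 1 − 0.98³ = 5.9%. The chance that at least one of n subjects does is 1 − 0.98^(3n): 59.7% for n = 15, 66.4% for 18, 70.2% for 20. The expected number of such subjects is 0.9, 1.1 and 1.2.

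**What one control failure is worth.** At 108 versus 54 sessions the test still passes with at most 3 test failures if no control failure is counted, and with at most 4 if one is counted.

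**Upper bound on the effect.** Assume independent sessions, and that every subject with a control failure is removed, replaced and has all sessions dropped. Every counted control session is then a success, so the control rate is 100% and the expected difference at a true 98% versus 98% moves from 0 to −2.0 points. Power becomes the chance that test failures stay within the limit for zero control failures. At 18 subjects that is P(at most 3 failures in 108 at 2%) = 0.113 + 0.249 + 0.272 + 0.196 = 0.829.

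| Subjects | Test/control sessions | Power, all sessions kept | Power, all affected subjects removed | Rejection at true 90% vs 98%: kept | Same: removed |
|---|---|---|---|---|---|
| 15 | 90/45 | 84.6% | 73.1% | 2.4% | 0.5% |
| 18 | 108/54 | 91.3% | 82.9% | 2.3% | 0.4% |
| 20 | 120/60 | 89.8% | 78.0% | 2.3% | 0.2% |

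Power is lower at 20 than at 18 because the test is discrete: with no control failure, both sizes allow 3 test failures.

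**Partial removal.** If only a quarter or a half of affected subjects are removed (assumed shares), power at 18 subjects is 89.7% or 87.9%.

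**Clustering.** The documents give no within-subject correlation, so these intraclass correlations (ICC) are assumptions. Each subject has a beta-distributed success probability, ranked the same way for both needles; there are 18 subjects.

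| ICC | Power: kept vs removed | Rejection at true 90% vs 98%: kept vs removed |
|---|---|---|
| 0.1 | 91% vs 89% | 3.0% vs 2.3% |
| 0.3 | 91% vs 95% | 6.1% vs 9.9% |

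At ICC 0.3 the direction reverses, because removing subjects with poor access also improves the test sessions that remain. The 6.1% is already above 2.5% with all sessions kept, because the pooled test ignores clustering; that is a separate matter.

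**The case against.** The case against is substantial. The harm needs three steps that no section states: that one session cut short means the control sessions were not completed, that leaving the subject count means leaving the analysis, and that the control outcomes are then discarded. Sections 8.1, 8.2, 10.1.2, 10.3.1 and 10.4.2 lean the other way. The rescreening example in 6.3 (waiting for a fistula to mature) fits the ineligibility limb, since inclusion criterion 4 requires mature access, so it does not show that a control failure triggers the rule. The list of data kept is not worded as exclusive, and Table 1 already records treatment success or failure at every control visit.

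Incomplete and failed are also not identical. A session stopped for patient illness is incomplete but counts as a success under 10.1.2. The completion reading would remove that subject too, and the calculation above does not model this.

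On size, the full power loss is a stacked worst case. With partial removal at 18 subjects, power stays above the planned 85%. One control failure changes the result only at the boundary: exactly one control failure with exactly four test failures has probability 0.370 × 0.105 = 3.9% at 98% success. The 60% to 70% figures are the chance that a control failure occurs, not the chance that 6.3 is misapplied.

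All of this limits the point but does not remove it. None of the sections that favour keeping sessions mentions screen failures or overrides 6.3, Section 8.2 says only that data may be used, and Section 10.2 is silent.

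A reader might go further and infer that the plan removes control failures in order to favour the V Needle, or that it inflates false non-inferiority. The documents do not support either. They do not say that screen failures' sessions are dropped. With independent sessions, removal works against the V Needle, and the sign under clustering depends on an assumed correlation.

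**Conclusion.** The point holds as an unresolved ambiguity that affects the primary comparison. As written, 6.3 can select subjects on the control outcome with no counterpart for test sessions. This sits uneasily with 8.1 and with the attempted-sessions denominator in 10.1.2, and no analysis set decides it.

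The size runs from nil, if all attempted sessions are analysed, to the upper bound of 8.4 points of power at 18 subjects (91.3 − 82.9), 11.5 at 15 (84.6 − 73.1) and 11.8 at 20 (89.8 − 78.0). That bound assumes independent sessions, 98% success on both needles, and removal and replacement of every affected subject. With clustering no direction is claimed.

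A control failure is more likely than not to occur. The study is open-label and the clinician judges the outcome, so whether such a session counts should be fixed before data are seen. The change should be made, but this is not a fatal flaw.

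**What to change.** Reconcile 6.3 with 8.1 and 10.1.2, so that the screen-failure label and the endpoint do not depend on an undefined notion of completing the control sessions. State in 10.2 that the primary analysis includes every attempted control and test session of subjects who met the eligibility criteria, by needle used, whether or not the subject is later labelled a screen failure under 6.3. Report how many subjects stopped before V Needle sessions, with reasons and control-session outcomes.

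Whether such a subject continues or is rescreened is left to the sponsor and investigators; the analysis rule does not depend on it.

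The cost is wording in two sections and one line of reporting. No new data are needed, because the Therapy Assessment Form in Table 1 already captures success or failure at control visits. The downside is that a few control-only sessions may enter the pooled analysis and shift the 2:1 ratio slightly.
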